4. PEES
5. Diet Counseling
6. Three-day diet diary
7. Concomitant Medications (review if baseline and screening visits do not take place on the same day)
8. Payment to Participant for Completed Visit

* Histological outcomes (e.g. maximum eos/hpf) will be assessed by an experienced study pathologist.

** All GI providers will be trained to assess EREFs prior to the initiation of the trial. They will complete the evaluation for all suspected cases of EoE.

Randomization

Participants will be randomized to either the DED or FREE diet.

Intervention

Participants will receive diet education. A trained nutritionist/dietician will provide counseling regarding the foods allowed and foods not allowed on each diet. Participants will be given written instructions and daily diet diaries for their own use.

Coordinator Telephone Contacts: (Weeks 2, 3, 5, 6, 8, 9, and 11; days 7 through 77)

Beginning with Telephone Contact at Day 7, the coordinator will assess AEs, review concomitant medications, review withdrawal criteria, and assess difficulty adhering to the diet. Participants will be sent invitations from REDCap to complete required questionnaires. The coordinator will remind participants to complete the questionnaires. The participant will be instructed to call the investigator if any intolerable and/or SAEs occur. If any change in the study medication is required, the participant should come in for a clinic visit as soon as possible.

Coordinator Call:

1. Diet/Medication Review & Adherence Assessment
2. Review concomitant medications
3. Review withdrawal criteria
4. Review previously reported AEs
5. Survey reminder

Dietician Telephone Contacts: (Weeks 1, 4, 7 and 11; days 7 through 77)

Beginning with Telephone Contact at Day 7, the Dietician will assess adherence to the diet, answer questions regarding the diet, assess changes in weight, and assess difficulty adhering to the diet.

Participant Questionnaires (Baseline, Week 4, Week 8, and Week 12; days 1 through 84)

Participant Questionnaires (via REDCAP)

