1 PROTOCOL SUMMARY

1.1 SYNOPSIS

Title:	Food Additive Removal Diet for Pediatric Eosinophilic Esophagitis (FREE)
Study Description:	Prospective, pragmatic standard of care clinical trial comparing dietary therapies of dairy elimination diet (DED) to dairy + food additive elimination diet (FREE) in children with eosinophilic esophagitis.
Objectives:	
Primary Objective: To compare histologic outcomes (eosinophils per high power field: eos/hpf) of dairy elimination diet (DED) to dairy + food additive elimination diet (FREE) in children with eosinophilic esophagitis.
 
Secondary Objective: To compare endoscopic outcomes (Eosinophilic Esophagitis Endoscopic Reference scores: EREFs) of dairy elimination diet (DED) to dairy + food additive elimination diet (FREE) in children with eosinophilic esophagitis
 
Tertiary Objectives: To compare symptomatic (Pediatric Eosinophilic Esophagitis Symptom Severity Module v2.0: PEES) and quality of life (Peds-QL EoE Module 1) outcomes of dairy elimination diet (DED) to dairy + food additive elimination diet (FREE) in children with eosinophilic esophagitis

Endpoints:	
Primary Endpoint: (1) Histologic change differences of maximum eos/hpf baseline vs 12 week endoscopy
 
Secondary Endpoint: (1) EREFs: Eosinophilic Esophagitis Endoscopic Reference Score baseline vs 12 weeks
 
Tertiary Endpoints: (1) Patient Reported Outcomes (Pediatric Eosinophilic Esophagitis Symptom Severity Module (PEES) baseline vs 12 weeks, (2) quality of life (PedsQL-EoE)¹ baseline vs 12 weeks

Study Population:	We will plan to enroll 72 patients. Based on histologic primary outcome efficacy estimates of DED (50%) compared to FREE (estimated 70%) and a sample size of 36 enrolled patients per group (72 total) with 88% power, we will be able to demonstrate a detectable difference of 30% among two

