3 OBJECTIVES AND ENDPOINTS

OBJECTIVES	ENDPOINTS	JUSTIFICATION FOR ENDPOINTS
Primary		
To compare histologic outcomes of DED and FREE among children with eosinophilic esophagitis	Maximum eos/hpf (primary)	Eosinophils are a biomarker of inflammation. Current diagnostic criteria specify ≥ 15 eos/hpf. A reduction in eos/hpf should correlate with a reduction in symptoms. A successful treatment outcome is < 15 eos/hpf.
Secondary		
To compare endoscopic outcomes of DED and FREE among children with eosinophilic esophagitis	Eosinophilic Esophagitis Endoscopic Reference Score (EREFs)(secondary)	Includes additional eosinophil morphology and associated histopathologic features (e.g. degranulation, microabscesses, superficial layering, basal zone hyperplasia)
Tertiary/Exploratory		
To compare quality of life and patient reported outcomes of DED and FREE among children with eosinophilic esophagitis	PedsQL-EoE (tertiary) Pediatric Eosinophilic Esophagitis Symptom Severity Module (PEESS) (tertiary)	Determines the impact of DED and FREE on QOL and symptom severity, which is not routinely assessed.

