5.3 STRATEGIES FOR RECRUITMENT AND RETENTION

Providers at participating sites will be educated on the study protocol. Local pathologists will notify study coordinators of patient eligibility. Samples from standard of care biopsies will be batch shipped to the lead site for analysis by the central pathologist. The samples will be identified by the study ID only. Only the originating site can link the codes to the patient.

M. Collin's recommended criteria for the diagnosis of eosinophilic esophagitis (EE) will be used to evaluate the esophageal biopsies.²⁴ The central pathologist, who has extensive experience in the diagnosis of EE will review all biopsies, blind to patient's dietary status. The grading and staging of EE will be based on Collin's criteria, especially to be focused on eosinophilic inflammation, epithelial basal zone changes, eosinophilic abscess, and lamina propria fibrosis. Samples will be returned to the originating sites after central pathology review.

Patients (or in the case of children, the pediatric patient and their parent/legal guardian) will be approached for participation after a clinical assessment has been performed by a GI provider. Study procedures will be performed after obtaining proper consent and/or child assent. In addition, the clinic schedule will be reviewed each week for potential participants. If possible, patients or families will be contacted ahead of time to determine their interest in the study, should they qualify for participation.

Participants will be paid the following: Baseline Visit \$25.00 + 2 weeks of surveys X \$25 + Final Visit \$50.00 = \$125.00 per participant. The telephone follow up and the participant questionnaires must be completed at each designated visit to receive payment. Gift cards will be mailed to participants upon the completion of each eligible visit.

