6.2 MEASURES TO MINIMIZE BIAS: RANDOMIZATION

A randomization table will be generated for each site via *randomization.com* and will be used for assigning eligible participants to a treatment regimen.

To enroll a participant (Visit 1), the investigator (or designee) will assign each participant a 5-digit number which serves as the participant identifier throughout the study.

To randomize a participant (Visit 1), the investigator (or designee) will notify the lead site that a participant has been enrolled. The lead site will randomize the patient.

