9.4 STATISTICAL ANALYSES

Primary analyses will assess effectiveness endpoints, including eos/hpf and EREFs. Efficacy variables will be summarized descriptively and compared between treatment groups.

Secondary analyses include descriptive statistics of the patient population (patient demographics, clinical characteristics, and comorbid conditions), concomitant medications used in this patient population and changes to these treatments.

Categorical variables will be described using frequencies and percentages while continuous variables will be described using means, standard deviations, medians, and inter-quartile ranges.

Independent sample t-tests will be conducted to compare outcomes between groups.

Additional analysis plans may be developed based on clinical considerations.

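### No masking to diet is stated for the GI provider who scores week-12 EREFs, and the plan labels EREFs primary in one place and secondary in two others

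*Combined protocol and SAP*

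**What the plan says.** **Who scores.** A footnote to the baseline procedures in Section 8 says "All GI providers will be trained to assess EREFs prior to the initiation of the trial", and then "They will complete the evaluation for all suspected cases of EoE". The schedule in Section 1.3 places the score at baseline and at week 12. The week-12 list in Section 8 puts it alongside the diet diary and the diet and adherence review, with no order of completion.

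**Who is masked.** Section 5.3 says that the central pathologist "will review all biopsies, blind to patient's dietary status". No other masking statement appears.

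**Who knows the allocation.** Section 6.2 says "The lead site will randomize the patient", after notice from the investigator or a designee. Section 8 gives diet counselling to a nutritionist or dietician. No text keeps the result from GI providers.

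**Status of EREFs.** The synopsis lists as its secondary endpoint "EREFs: Eosinophilic Esophagitis Endoscopic Reference Score baseline vs 12 weeks", and the table in Section 3 also marks it secondary. Section 9.4 says "Primary analyses will assess effectiveness endpoints, including eos/hpf and EREFs". Section 9.1 hypothesises superiority of FREE for primary and secondary endpoints alike.

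**The concern.** EREFs is a judgement made by looking, in a trial where families know which diet they follow and the investigators have said which diet they expect to do better. A scorer who knows the diet may grade borderline findings in the expected direction without intending to. The plan guards against this for histology but writes no equivalent for endoscopy.

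If FREE showed an advantage on EREFs, a reader could not separate a diet effect from scorer expectation, and nothing collected under the plan would show how many scorers knew the diet. The conflicting labels raise the stakes: under the wording of Section 9.4, a favourable EREFs result could be presented as a primary finding.

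**Working it through.** **1. The plan's own figure.** The documents give no power, SD or expected difference for EREFs. The only power figure, 88% in Section 9.1, is for histology: 50% versus 70%, SD 30%, 36 per group. Treated as a comparison of means, z = (20/30) × √(36/2) = 2.828.
- One-sided 5%: Φ(2.828 − 1.645) = 88.2%, which matches.
- Two-sided 5%: Φ(2.828 − 1.960) = 80.7%, which does not.

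Masking changes none of these numbers. They matter here only because neither alpha nor sidedness is stated, so step 3 gives both cases.

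**2. Where a bias would enter.** GI providers score all suspected cases, so the baseline score appears to come from the diagnostic endoscopy, before allocation. The exposure is therefore mainly at week 12. If scoring shifts the week-12 mean by *b* in one arm relative to the other, then

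difference in mean change = (true difference + *b*) − 0,

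because the baseline carries no matching shift. Subtracting baseline does not remove *b*.

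**3. Illustration of size.** Assumptions, none from the documents: the true difference is zero, the net scoring shift toward one arm is *b* SD of the analysed score, and alpha is 5%. The independent-samples t-test (Section 9.4) then follows a non-central t with non-centrality *b*√(n/2) and 2n − 2 degrees of freedom. The value n = 36 is from Section 9.1. The value n = 29 comes from the synopsis dropout of 20%: 36 × 0.8 = 28.8.

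Example: *b* = 0.2 and n = 36 give non-centrality 0.2 × √18 = 0.849, with a two-sided critical value of 1.994 on 70 degrees of freedom. The rejection probability is 13.3%.

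| Assumed shift | 36 per arm, two-sided | 29 per arm, two-sided | 36 per arm, one-sided toward FREE |
|---|---|---|---|
| 0.1 SD | 7.0% | 6.6% | 11% |
| 0.2 SD | 13.3% | 11.6% | 21% |
| 0.3 SD | 24.1% | 20.2% | 35% |

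The normal approximation gives 7.1%, 13.6% and 24.7% in the first column, so the method makes little difference.

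**4. What the documents allow on masking.** In favour: the lead site randomises, dieticians counsel, coordinators and dieticians make the adherence calls, and no listed procedure requires the endoscopist to know the diet before scoring. Against:
- GI providers assess patients before enrolment (Section 5.3).
- A provider may stop the study diet (Section 7.1).
- GI providers join the monthly safety review and consider participant-level data (Section 10.1.5).
- Remote participants' records come from a local provider (Section 10.1.4), and nothing says who scores their EREFs.

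The text does not say whether the week-12 endoscopist is the patient's own provider.

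**The case against.** **The primary endpoint is protected.** Maximum eos/hpf is the only listed primary endpoint, and the central pathologist reads it blind. This stands, and it confines the point to EREFs.

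**Section 9.4 may be grouping analyses, not endpoints.** Its secondary analyses are descriptive summaries of the population and medications, so its primary heading may simply mean efficacy. A reader might infer that EREFs is co-primary; the synopsis and Section 3 do not support that. The labels still need to agree, and the superiority hypothesis covers EREFs under either one.

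**Silence is not evidence of unmasked scoring.** A reader might infer that scorers know the diet. The documents say neither that they do nor that they do not. What can be said is that no masking is stated and nothing prevents disclosure.

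**Masking may not be free.** A reader might infer that the existing endoscopist can be masked everywhere with no additional reader. Given GI providers' roles in care and safety review, that is not shown. Full masking could need a second endoscopist or a reader of recorded images. Partial masking with existing staff remains feasible.

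**The shifts are assumed.** Both arms are active dairy-free diets, so the size and even the direction of any expectation bias are uncertain, and the same table would apply to any unmasked score. This stands.

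**It is a pragmatic trial.** Scoring by trained clinicians is a recognisable choice in such a design. That justifies who scores; it does not justify leaving masking and its failures unrecorded.

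**Conclusion.** The point holds in limited form. The plan states no masking for week-12 EREFs, although it masks histology and expects FREE to do better on EREFs too, and it labels the endpoint inconsistently. This should be corrected; it does not threaten the histologic primary endpoint.

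The size is unknown. Type I error of about 7%, 13% and 24% (two-sided 5%, 36 per arm) follows from assumed net shifts of 0.1, 0.2 and 0.3 SD with no true effect. A reader might take these as estimates of this trial's error rate, but the documents contain nothing from which to estimate the shift.

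**What to change.** **Section 8.** State that:
- the endoscopist scoring week-12 EREFs is not told the assigned diet, where the site's existing staffing allows;
- families are asked not to disclose the diet before scoring;
- the form is completed at endoscopy, before diet diaries, the adherence review or histology are seen;
- the form records whether the scorer knew the diet.

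**Section 9.4.** Label EREFs secondary, to match the synopsis and Section 3, and report the proportion of unmasked scores by arm. Any analysis restricted to masked scores should be called descriptive. Whether the scorer learned the diet is settled after randomisation and may differ by arm or outcome, so the subset is not a randomised comparison. It would also be smaller than the roughly 29 per arm expected after dropout.

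**Cost.** Wording in two sections, one field on the form and one tabulation; this partial version needs no new staff or procedure.

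**Downside.** Masking will be incomplete where the endoscopist is the treating provider or the participant is remote. This version is dated 22 July 2020 and the synopsis gives 31 July 2020 as the end of the study period, so unless the timeline moved, few week-12 scores may remain to be masked, and those already recorded cannot be. Both limits must be reported.

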	
group comparisons. We estimate a 20% drop out rate among the diet elimination groups and analysis based on intention to treat.
 
Patients ≥ 2 - 18 years of age with isolated esophageal eosinophilia (≥ 15 eos/hpf). Patients with peripheral eosinophilia $> 1,500 \mu\text{L}$, concomitant GI inflammatory conditions, history of upper GI tract surgery (e.g. fundoplication), acid reflux by pH probe, severe developmental delay, have other medical conditions likely interfere with the study, has a significant psychiatric condition, has taken swallowed steroids in the last 8 weeks, or are not fluent in spoken and written English will be excluded.

Description of Sites/Facilities Enrolling Participants:
	
Participants will be enrolled nationally.

Description of Study Intervention:
	
Once patients meet eligibility criteria, they will be randomized to DED or FREE study groups. Participants will receive dietary education. Lead dietitians from each site will be identified and the approaches to dietary education will be standardized. Dietary education will be completed at the baseline visit and during follow up phone calls throughout the study.

Study Duration:
	
We anticipate this study will take 30 months to complete.
 
[December 31, 2017-----July 31, 2020]
 
Pre-trial Activities [-----] 7 mos
 
Enrollment/Intervention [-----] 16 mos
 
Data Collection [-----] 19 mos
 
Data Analysis [-----] 4 mos

Participant Duration:
	
Each participant will complete all study visits in 12 weeks +/-14 days.

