9.3 POPULATIONS FOR ANALYSES

Safety analysis will be conducted on all patients evaluable for safety, defined as those patients who received any amount of study drug and provide any post-treatment safety data.

Efficacy analyses will be conducted on the intent-to-treat population, defined as all patients enrolled in the study who received patient IDs regardless of whether they received study drug or not.

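### PedsQL-EoE and PEESS are collected at weeks 4, 8 and 12, but the only named comparison is a baseline-to-week-12 t-test, with no baseline adjustment and no missing-data rule

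*Combined protocol and SAP*

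**What the plan says.** - **Collection.** Section 8 schedules PEESS and PedsQL-EoE as "Participant Questionnaires (Baseline, Week 4, Week 8, and Week 12; days 1 through 84". The Schedule of Activities (1.3) agrees and marks the week-4, week-8 and week-12 entries as REDCap surveys.
- **Endpoints.** The Synopsis (1.1) lists "Patient Reported Outcomes (Pediatric Eosinophilic Esophagitis Symptom Severity Module (PEES) baseline vs 12 weeks" and then quality of life by PedsQL-EoE over the same interval. Section 3 labels both tertiary/exploratory.
- **Test.** Section 9.4: "Independent sample t-tests will be conducted to compare outcomes between groups". No other inferential method is named. The section also says "Additional analysis plans may be developed based on clinical considerations".
- **Population and dropout.** Section 9.3: "Efficacy analyses will be conducted on the intent-to-treat population, defined as all patients enrolled in the study who received patient IDs". The Synopsis adds "We estimate a 20% drop out rate among the diet elimination groups" and says that analysis is by intention to treat.
- **Withdrawal.** Section 7.1 requires withdrawal from the study of children who cannot tolerate the diet or who cannot or will not keep to it. It also asks investigators to try to obtain information on those who leave and, for those lost to follow-up, to try to complete the final evaluation.

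No section describes an analysis of the week-4 or week-8 scores, a baseline covariate, or how a missing week-12 score is handled.

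**The concern.** A two-sample t-test on week 12, whether on the score or on its change from baseline, needs a week-12 value from every child it includes. The plan claims intention to treat and expects one child in five to drop out, but gives no way for a child without that value to count, even when the child has supplied weeks 4 and 8.

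Two things are at stake. The first is precision: an unadjusted change score wastes information held in the baseline. The second is bias. Withdrawal for non-adherence is mandatory, and FREE adds a restriction to DED. Dropout could therefore differ by arm and depend on how a child was doing earlier. If children who worsen early on FREE leave, the remaining FREE children look better than the arm as randomised. Section 3 says these outcomes are meant to show the diets' effect on quality of life and symptom severity, and such a loss would distort that comparison.

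**Working it through.** **Plan's own figure.** No power or sample size is stated for the questionnaires. The 88% in Section 9.1 concerns the histologic outcome. With a difference of 20, SD 30 and 36 per arm, 20/(30·√(2/36)) = 2.83. Less 1.645, this gives 88.2% at one-sided 0.05; the two-sided figure is 80.7%. It has no bearing on this point.

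**Inputs.** From the documents: 36 per arm, 20% dropout, visits at weeks 0, 4, 8 and 12. Assumed, because the documents give none: equal SD (set to 1) at every visit; correlation r of 0.4-0.8, either compound symmetry (CS) or first-order autoregressive (AR); dropout of 7%, 7% and 6% in successive intervals. The t-test is assumed to be on change among completers.

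**Children affected.** 0.20 × 72 = 14.4, so about 14 children have no week-12 score; 0.80 × 36 = 28.8 per arm remain.

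**Precision.** Let ρ be the baseline-to-week-12 correlation (r under CS, r³ under AR).

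- Completer t-test on change: variance = 2·2(1−ρ)/28.8.
- Completer comparison adjusted for baseline: variance = 2(1−ρ²)/28.8.
- Their ratio is (1+ρ)/2, so baseline adjustment alone saves (1−ρ)/2.
- Repeated-measures model: the information from each dropout pattern (all visits; to week 8; to week 4; baseline only) is summed over children and inverted, and the week-12 contrast is read off.

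| Assumed correlation | ρ | Saved by baseline adjustment | Further saving from interim visits | Total |
|---|---|---|---|---|
| CS 0.8 | 0.80 | 10.0% | 3.3% | 1 − 0.900 × 0.967 = 13% |
| AR 0.8 | 0.512 | 24.4% | 5.0% | 1 − 0.756 × 0.950 = 28% |
| AR 0.4 | 0.064 | 46.8% | 1.2% | 1 − 0.532 × 0.988 = 47% |

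The range is about 13-47% in total, with about 1-5% from the interim visits.

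**Cross-check as effective sample size** (correlations 0.3-0.8, all analyses conditional on baseline). Against 28.8 completers per arm, the repeated-measures model is worth:

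- 29.0-30.4 if dropout is spread evenly;
- 29.3-32.1 if it all follows week 8;
- 28.8 if it all precedes week 4.

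The gain is 0 to 3.3 children per arm.

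**Bias.** Assumed scenario: no true effect, 14% random dropout on DED, and 25% on FREE with probability rising with week-4 worsening (average 19.5%, close to the planned 20%). Large simulations, with moderate to strong dependence, give:

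- completer t-test on change: about 0.1-0.2 SD in favour of FREE;
- completers with baseline adjustment only: about 0.05-0.10 SD in favour of FREE;
- baseline and week 4 both used: about 0.

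The last result is expected. Given baseline and week 4, those who leave and those who stay have the same expected week-12 score in this scenario.

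**The case against.** **The interim visits buy little precision.** This stands. A reader might infer that ignoring weeks 4 and 8 costs much of the information. It does not: the large part of the saving comes from baseline adjustment, which needs no interim visit.

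**The comparator is inferred.** This also stands. Section 9.4 does not say change score, does not say completers only, and reaches the questionnaires only through the word outcomes. A t-test on the week-12 score would give different variances. Either form still needs a week-12 value.

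**Leaving the diet is not the same as having no week-12 score.** This stands in part. The surveys are remote, and Section 7.1 asks staff to seek information after withdrawal. A child who supplies week 12 would count. A reader might infer that every early leaver is lost; the documents support only that no rule covers those whose week-12 score is missing.

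**The bias scenario is constructed.** This stands. The documents give no dropout by arm and no link to earlier scores, so an actual bias cannot be claimed. The size is also modest: in units of the SD of change, one standard error with 28.8 per arm is √(2/28.8) = 0.26.

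**A mixed model is not automatically the intention-to-treat answer.** This stands. Under missing at random it treats leavers as continuing like comparable stayers, which is doubtful when non-adherent children must be withdrawn. A sensitivity analysis is therefore needed.

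**The endpoints are exploratory, and 9.4 permits further analyses.** The first part limits the importance. The second does not close the gap, because the clause pre-specifies nothing.

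**Conclusion.** The point holds as a minor, free improvement. Four collection times, a baseline-to-week-12 endpoint, a t-test as the sole named method and the absence of a missing-data rule are all plain in the text. They do not show how the declared population is achieved with about 14 of 72 children expected to drop out.

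The size rests on assumptions. With correlations of 0.4-0.8, 20% dropout and a completer t-test on change as comparator, the week-12 variance falls by about 13-47%, nearly all from baseline adjustment. The case for using weeks 4 and 8 is protection against bias if dropout depends on earlier scores: about 0.1-0.2 SD in the assumed scenario, against about 0.05-0.10 SD with baseline adjustment alone and none once week 4 is included.

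A reader might go further and conclude that the trial's main result is at risk, or that these outcomes measure tolerability. Neither is supported: the primary endpoint is eosinophil count, and Section 3 gives the purpose of the questionnaires as quality of life and symptom severity.

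**What to change.** In Section 9.4, for PedsQL-EoE and PEESS:

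1. Pre-specify a mixed model for repeated measures on weeks 4, 8 and 12, with baseline score, arm, visit and arm-by-visit interaction. Section 6.2 randomises by site, so a site term is natural, but the number of sites is not stated; include it only if numbers allow.
2. Report the week-12 between-arm contrast as the tertiary estimate. The endpoint definition does not change.
3. Keep the t-test as a supportive analysis, stating whether it uses the change or the week-12 score and which children it includes.
4. Add a sensitivity analysis for data not missing at random, for example shifting the unobserved week-12 scores of withdrawn children towards worse values by a range of amounts. Report the number and timing of missing scores by arm.

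The cost is SAP wording and a little analysis time. No new visit, survey or participant burden is involved. The text should be fixed before scores are compared by arm; if that has already happened, the model should be labelled post hoc.
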